6.4. Data Analysis

6.4.1. Primary Analyses

We will conduct primary analyses to assess the effect of the randomized interventions on drug concentrations at 9-months post-randomization by 1) comparing the first-stage intervention options on TFV-DP levels at the 9-month visit; 2) comparing the second-stage intervention options on TFV-DP levels at the 9-month visit among participants classified as “non-responders” to the initial intervention; and 3) comparing the four adaptive intervention strategies described in Table 1.

For the analyses of first-stage intervention options, logistic regression will be used to assess effect of the each primary randomized intervention on 9-month adherence by comparing TFV-DP levels in Groups 1-3 versus Groups 4-6 shown in Figure 1B on page 10. For the analyses of second-stage intervention options among non-responders, logistic regression will also be used to assess the effect of the intensified adherence intervention (second randomization) within each arm of the first randomization, and in the absence of interaction, pooled across the first randomization (Groups 2 and 5 versus Groups 3 and 6). For analyses comparing the adaptive intervention approaches, each of the 4 overall strategies (2 initial x 2 intensification interventions in non-responders) will be ranked by their overall adherence response (Table 3), with inverse-probability weighting and standard errors taking into account that women who respond to their first-assigned treatment are consistent with *two* of strategies embedded within our SMART design and over-represented in our analysis datasets. Because of the high expected post-randomization drop-out before M1, we will adjust for confounders of PrEP continuation and adherence and M1 drop-out in the analysis.

Table 3. Combination of adherence intervention strategies in SMART design. [Note that under each of the four strategies embedded in our trial design, young women who are adhering (“responding”) will continue to receive their originally-assigned method of support (i.e., WhatsApp groups or weekly two-way SMS).]

Standard of care brief counseling and one-way SMS reminder messages with WhatsApp peer support, followed by quarterly drug level counseling for non-responders
Standard of care brief counseling and one-way SMS reminder messages with WhatsApp peer support, followed by monthly visits with problem-focused counseling for non-responders

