Statistical Analysis Plan

Version 1.5

Evaluation of stepped PrEP adherence support for young South African women using a SMART design

Short Title: *PrEP SMART*

9 May 2022

Drafted by: [name] MPH; [name]; [name]

Statistical Team

University of Washington, Seattle, USA

[name]

[name] MPH

[name]

[name]

[name], MS

University of the Witwatersrand, Johannesburg, South Africa

[name]

Investigators

[name], MPH *University of Washington, Seattle, USA*

[name], PhD, *University of the Witwatersrand, Johannesburg, South Africa*

[name], PhD, *University of Washington, Seattle, USA*

[name], *Stroger Hospital of Cook County, Chicago, USA*

Table of Contents

Background and Rationale	3
Study Objectives and Hypothesis	3
Study Design	4
Schema	6
Overview of Study Design	8
Sample size and power calculations.....	10
Data Analysis.....	10

Background and Rationale

The purpose of this study is to test a stepped model of scalable adherence support strategies in young South African women who initiate PrEP using a sequential multiple assignment randomized trial (SMART) design.

A SMART is a useful experimental design for the development of high-quality adaptive interventions. The SMART design utilized in this study will allow us to evaluate which of four embedded dynamic treatment strategies achieves highest PrEP adherence.

Study Objectives and Hypotheses

The primary objectives of this study are:

- To evaluate the effect of the mHealth interventions, in addition to regular clinic visits, on PrEP adherence at the nine-month study visit.
- To evaluate the effect of the additional adherence support interventions, in addition to regular clinic visits and first-line mHealth interventions, on PrEP adherence at the nine-month study visit, separately for (1) non-responders to the first-line SMS intervention and (2) non-responders to the first-line WhatsApp intervention.
- To evaluate the four embedded dynamic treatment strategies in terms of PrEP adherence at the nine-month study visit to identify the best adherence support strategy.

The secondary objectives of this study are:

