- 2) Primary analysis: We will use modified Poisson regression to assess the effect of the randomized second-line intervention on 9-month adherence by comparing TFV-DP levels across participants receiving monthly counseling versus participants receiving drug-level feedback, separately for (1) non-responders to the first-line SMS intervention and (2) non-responders to the first-line WhatsApp intervention. The effect of the randomized intervention will be estimated as a relative risk (RR) from the regression models, with study arm assigned at second randomization as the predictor of interest and robust standard error estimates.

Sensitivity analysis: If overall loss to follow-up in the full sample is $> 10\%$ by month 9 or if differential loss to follow-up between the two arms is $> 10\%$, we will repeat the primary analysis using inverse probability weights to adjust for the potential impact of censoring due to missing data.

Subgroup analysis: Subgroup-specific estimates of the intervention will be generated using the same models and analysis population as described in the primary analysis (above) but will also include subgroup indicator variable(s) and an interaction term between the subgroup indicator and second-line study arm in the model. Subgroups will be defined as follows:

- Age ≤ 20 years versus > 20 years
- 3) Secondary analyses:
 - We will also assess the effect of the intervention on the continuous PrEP adherence outcome using linear regression models to assess the difference in mean TFV-DP levels between those in the monthly problem-focused counseling group and those in the drug-level feedback group at month 9. If less than 40% of the sample has drug undetectable drug levels, we will assign those with undetectable drug levels a numeric drug level equal to half the limit of detection. If more than 40% of the sample has undetectable drug levels, we will reassess the value of this analysis.

- We will also consider evaluating the effect of second-line treatment stratified by reason for non-response; however, if the number of participants available for these stratified analyses is insufficient, we will not pursue these analyses.

Primary Analysis 3: Among the embedded dynamic treatment strategies, identify the optimal adherence support strategy in terms of PrEP adherence at the nine-month study visit, where additional adherence support is provided to those who have low adherence after the first two months of PrEP use.

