Analysis population: All PrEP SMART participants. For a secondary modified intent-to-treat analysis, we will include only participants who attend at least one study visit between months 1-3.

Outcome: PrEP adherence at the nine-month study visit, defined as a binary outcome variable around TFV-DP levels of 700 fmol/punch

Predictor(s) of interest: Embedded dynamic treatment strategies

Statistical analyses:

- 1) We will estimate the proportion of participants adherent to PrEP for each of the four embedded dynamic adherence support strategies (as shown in Table 1) and will compare the proportion adherent to PrEP across the four groups.
 - a. We will pursue a weighted-and-replicated approach to account for non-response and re-randomization as well as overlap in dynamic treatment regimes (Kidwell et al., *J Appl Stat*, 2018). The weighted-and-replicated approach involves two steps:
 - i. Weighting: In a SMART, for a given embedded dynamic treatment strategy, there is imbalance in the responders and non-responders who followed the strategy. In particular, assuming 1:1 randomization in each of the two phases of the SMART, the chance of a responder following the strategy is 0.5, while the chance of a non-responder following the strategy is $0.5 \times 0.5 = 0.25$. Thus, responders are over-represented, by design. However, all participants should be equally represented. To achieve this, we assign a weight of $1/0.5 = 2$ to responders and $1/0.25 = 4$ to non-responders. We must also use robust standard error estimates because the weights depend on responder status, which is unknown ahead of time.
 - ii. Replicating: If we would like to compare two embedded dynamic treatment strategies that have the same first-line treatment, we have to account for the fact that one participant can be in two treatment strategies. Namely, in PrEP SMART, if a participant is a responder to one first-line treatment, they are automatically in two embedded treatment strategies. Thus, to model the data, we have to replicate this person's observation (i.e., make a copy of their row in the dataset). Non-responders are not replicated as they only follow one embedded dynamic treatment strategy. Note that this is not needed if we are evaluating embedded dynamic treatment strategies that begin with different first-line treatments.

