    estimate 'DTS1' int 1 X1 0 X2 0 X1*X2 0 / exp;
    estimate 'DTS2' int 1 X1 0 X2 1 X1*X2 0 / exp;
    estimate 'DTS3' int 1 X1 1 X2 0 X1*X2 0 / exp;
    estimate 'DTS4' int 1 X1 1 X2 1 X1*X2 1 / exp;
    contrast 'globalnull' X1 1,
                        X2 1,
                        X1*X2 1 / e;

run;

```

- The 'estimate' statements will provide estimates of the probability of adherence (response) for each of the 4 embedded DTS, along with 95% CIs.
- The 'contrast' statement is a test of the global null hypothesis that the 4 embedded DTS are equal. The 'e' option will produce the contrast matrix, which should be checked to ensure the appropriate test is being done.

- 2) We will also include inverse probability weights to account for censoring if overall loss to follow-up in the full sample is >10% by month 9 or if differential loss to follow-up between the two arms is >10%.
- 3) Secondary analysis: We will conduct a modified intent-to-treat analysis using the same procedures described above (i.e., the weighted and replicated approach) but restricting to participants who returned for at least one study visit between months 1 and 3.
 - Since this analysis breaks randomization, we will adjust for important prognostic variables (including demographics, sexual behavior factors, and HIV risk factors) to account for treatment imbalances.

Secondary Analysis 1: Evaluate (1) the effect of the mHealth interventions on early PrEP adherence (month 2), (2) the effect of the mHealth interventions on long-term PrEP adherence (month 12) and (3) the effect of the additional adherence support interventions (second-line interventions) on long-term PrEP adherence (month 12) separately for (a) non-responders to the first-line SMS intervention and (b) non-responders to the first-line WhatsApp intervention

Analysis population:

- All individuals randomized to two-way SMS or WhatsApp groups who have drug levels available at month 2 and/or month 12.

- All individuals randomized to either monthly counseling or drug-level feedback who had drug levels available at month 12.

Outcome: PrEP adherence at the 2- and 12-month study visits, defined as a binary outcome variable around TFV-DP levels of 700 fmol/punch

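### Primary Analysis 3 sets out to identify the optimal strategy, but one global test and four separate intervals cannot show which strategy is best

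*SAP*

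**What the plan says.** The aim is selection. The third primary objective in the SAP (Study Objectives and Hypotheses) is to evaluate the four embedded strategies "to identify the best adherence support strategy", and the title of Primary Analysis 3 repeats it: "identify the optimal adherence support strategy in terms of PrEP adherence at the nine-month study visit". Protocol 6.4.1 gives the means of selection: the strategies "will be ranked by their overall adherence response (Table 3), with inverse-probability weighting". The word ranked is in the protocol only. The SAP says that it "will compare the proportion adherent to PrEP across the four groups".

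The SAP code for Primary Analysis 3 fits a weighted, replicated GEE with a log link and produces two things. The first is an estimate of the probability of adherence "for each of the 4 embedded DTS, along with 95% CIs". The second is a single contrast: "The 'contrast' statement is a test of the global null hypothesis that the 4 embedded DTS are equal".

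Neither document writes out a comparison of each strategy with the best, adjusts for multiple comparisons between strategies, or says what will be concluded if the global test does not reject. Primary Analyses 1 and 2 compare the component interventions, not the strategies.

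**The concern.** The question is which strategy is best. The test asks whether all four are equal. A rejection says that at least one pair differs, possibly the two at the bottom of the ranking, and does not single out the one at the top. The four intervals are marginal: each describes one strategy, and none describes a difference.

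The largest of four estimates is also a selected value, so it tends to be too high. At stake is one of three primary conclusions in the SAP: a recommended sequence of adherence support, put forward with no statement of how well it is separated from the alternatives.

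**Working it through.** **1. The nearest figure in the plan.** The documents give no power, error rate or probability of correct selection for Primary Analysis 3. The nearest figure is the first-stage power in Protocol 6.3: 60% vs 40%, 175 per arm, one-sided 0.025.
- SE under the null: sqrt(2 × 0.25/175) = 0.0535. SE under the alternative: sqrt((0.24 + 0.24)/175) = 0.0524.
- z = (0.20 − 1.96 × 0.0535)/0.0524 = 1.82, so power is 96.6%. The plan states 96%, so this figure is reproduced. It concerns first-stage response at month 2, not the strategies at month 9.

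**2. Inputs.**
- From the documents: 350 women, 175 per first-line arm; weights 2 for responders and 4 for non-responders; response 40% (SMS) and 60% (WhatsApp); second-stage adherence 40% (monthly visits) vs 25% (drug-level feedback).
- Assumed, because the documents do not give them: month-9 adherence in responders (55% to 80%), a 5% level for the global test, and complete data.

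**3. Precision of one strategy.** With response rate r and strategy mean p,

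Var = [r × E((y − p)² | responder) + 2(1 − r) × E((y − p)² | non-responder)]/175.

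For a null case take r = 0.5 and adherence of 55% in responders and 25% in non-responders, so p = 0.40.
- Responders: 0.2475 + 0.0225 = 0.27. Non-responders: 0.1875 + 0.0225 = 0.21.
- Var = (0.135 + 0.21)/175 = 0.00197, so the SE is 4.4 points.
- Two strategies with the same first-line arm share responders: correlation 0.135/0.345 = 0.39.
- SE of a difference: sqrt(2 × 0.21/175) = 4.9 points within a first-line arm, and sqrt(2 × 0.00197) = 6.3 points across arms. Even an unadjusted comparison therefore needs 9.6 or 12.3 points (1.96 × SE).

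**4. Four equal strategies (simulated).** At 40%, the best-to-worst gap averages 8 to 9 points, with a 95th percentile of 15 to 16. The top estimate exceeds its true value by about 4.3 points. The global test rejects in about 5%, so it holds its level. At 45%, at least one of the six unadjusted pairwise tests is significant in 20% of trials.

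**5. The protocol's effects.** A strategy mean is r × responder adherence + (1 − r) × non-responder adherence. With 55% in responders:
- SMS, monthly: 0.4 × 0.55 + 0.6 × 0.40 = 46%
- SMS, feedback: 0.4 × 0.55 + 0.6 × 0.25 = 37%
- WhatsApp, monthly: 0.6 × 0.55 + 0.4 × 0.40 = 49%
- WhatsApp, feedback: 0.6 × 0.55 + 0.4 × 0.25 = 43%

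The best leads the second by 3 points, against a 95th-percentile chance gap of about 15.

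One run of the weighted estimator with participant-level robust covariance gave the results below (4,000 trials per row; 1,500 for the 95% set of strategies not distinguishable from the best).

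| Responder adherence | Global test rejects | True best ranked first | Top is not the true best, given rejection | Mean size of set | Set has one member |
|---|---|---|---|---|---|
| 55% | 42.6% | 63.5% | 31.7% | 3.15 | 2.5% |
| 60% | 45.0% | 67.0% | 26.8% | 3.07 | 3.5% |
| 70% | 50.8% | 76.2% | 17.8% | 2.95 | 6.6% |
| 80% | 56.2% | 78.5% | 17.0% | 2.83 | 7.2% |

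Repeat runs differ by up to about 3 points. The ranges given elsewhere (43-57%, 63-80%, 14-32%) span them. After a rejection the top estimate is still about 4 to 4.5 points too high. When all four strategies are equal, the set names a single best in under 1% of trials.

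**The case against.** A reader might infer that the plan will declare a winner even when the strategies are identical. The documents do not say so. The SAP prescribes a test of exactly that situation and, used as a gate, it holds a false winner to about 5%. What is missing is the statement that it is a gate.

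A reader might also infer that nothing in the plan compares one strategy with another. That goes too far. In the SAP's model, β1 is the log relative risk of WhatsApp/monthly vs SMS/monthly, and β2 that of SMS/feedback vs SMS/monthly. The log link is chosen to estimate relative risks, and the SAP discusses comparing two strategies with the same first-line treatment. But the remaining contrasts are not written out, none is framed as a comparison with the best, and multiplicity is not addressed.

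Nor does sharing of responders make reading the intervals by eye liberal. The correlation is positive and affects two of the six pairs, so judging by overlap errs on the conservative side; it is simply not the right interval for a difference. Replication and clustering by participant already handle the sharing within the model.

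Three further points stand. The objective is one of several: the SAP sizes the trial on SMS vs WhatsApp, and Protocol 2.2 lists the optimal sequence as secondary, although the protocol schema and the SAP list it as primary. The month-9 rates are assumptions, and the results move with them. And a wrong choice can be cheap: with 55% in responders, taking the top-ranked strategy costs on average about 1.3 points of adherence against the true best.

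**Conclusion.** The concern holds in this form: the aim is to name the best of four strategies, and the specified analysis can reject equality but cannot support that naming. An explicit gate would deal with four equal strategies. It would not deal with the case the protocol expects, where about one rejection in seven to one in three comes with the wrong strategy on top.

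The figures rest on 350 women with complete data, a 5% global test and assumed responder adherence of 55-80%. Protocol 6.4.1 expects high early drop-out without giving a rate; fewer evaluable women would make the selection less certain. The estimator itself is not in question. This is an inexpensive improvement that should be made before the analysis, not a fault that invalidates it.

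**What to change.** Add to Primary Analysis 3 in the SAP, and align Protocol 6.4.1 with it:

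1. From the same weighted GEE and robust covariance, carry out multiple comparisons with the best. Report the 95% set of strategies not distinguishable from the best, with simultaneous confidence intervals for the differences from the best.
2. State the level of the global test and that, if it does not reject, no strategy is called optimal.
3. If it rejects, report the top-ranked strategy together with the set. Describe it as established best only if the set has one member.
4. State that the top strategy's estimated adherence is subject to upward selection bias, which the set does not remove.

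The cost is a paragraph of SAP text and a few lines of code, with no new data and no change of design. The downside is that the trial will usually report about three candidate strategies, and a one-member set will be rare (about 3-7% of trials under the protocol's effects). For that reason the third rule governs the wording of the conclusion and does not prevent the ranking from being reported.

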4.2.4. Month 3 randomization visit

Women with high adherence (i.e., TVF-DP ≥ 500 fmol/punch based on Month 2 drug levels) who have not missed PrEP refills at Month 1 or 2 will be considered ‘responders’. Responders will move to quarterly visits and continue to be offered the adherence support they were randomized to at enrollment. Pharmacy refills will be verified using electronic pharmacy records.

‘Non-responders’ (i.e., TFV-DP < 500 fmol/punch or missed PrEP refill) will be randomized to a more intensive adherence support – continued monthly counseling visits or quarterly visits with counseling based on drug levels at months 3 and 6. Randomization will be conducted with a ratio of 1:1 between the two study arms. We will use envelopes in order to assign “non-responding” subjects to the second intervention. Envelopes will be prepared by study staff in Seattle and site staff in Johannesburg will open the envelopes in the specified order only when they are ready to randomize a “non-responding” participant.

All women will continue with the intervention they were assigned in their initial randomization (WhatsApp groups or two-way SMS) regardless of if they are classified as responders or non-responders. Additional month 3 visit procedures are included in section 4.2.5.

[figure not shown]
In the case of public health emergencies, study procedures that require in person visits may be delayed, including blood draws to determine secondary randomization. Therefore, secondary randomization may be conducted using blood drawn from visits occurring between months 1 and 3.

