6.3. Accrual, Follow-up, and Sample Size

For the SMART trial design, the goal is to enroll and randomize up to 500 women in order to achieve an analysis sample size of approximately 350 women who return for their one-month study visit and will want to continue PrEP for a further 9 months: 175 per arm randomized into the first intervention at enrollment, continuing past their 1-month study visit and evaluable at 9 months. Up to 500 women who initiate PrEP will be enrolled over a period of approximately 18 months. 350 evaluable women

would have 96% power for the initial randomization to detect an increase from 40% response at 2 months to SOC + two-way SMS to 60% with the SOC + WhatsApp groups. Among the estimated 70-105 non-responders in each initial group, we have 79-96% power in each group of non-responders to detect a 30% difference in adherence at 9 months between women randomized to monthly counseling or drug level feedback. Pooling across the initial randomization, with 149-166 women we would have ~80% power to detect ~ 15-20% difference (Table 2).

Table 2: Power to assess differences in adherence by intervention strategies in each of the first and second stages using a one-sided $\alpha = 0.025$.

First Randomization			Second randomization (Pooled across first randomization)			
% Adherent				% Adherent		
WhatsApp + SOC N = 175	SMS + SOC N = 175	Power	Non-responders Total N	Monthly visits	Drug Level Counseling	Power
65%	40%	99%	166	40%	25%	84%
				50%	30%	89%
60%	40%	96%	175	40%	25%	86%
				50%	30%	91%
55%	40%	84%	184	40%	25%	88%
				50%	30%	91%

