The replicated data are then modeled using a weighted GEE with an independence working correlation matrix where the clusters are the individual subjects. The model can be written as:

$$\log(p) = \beta_0 + \beta_1 x_1 + \beta_2 x_{2NR} + \beta_3 x_1 x_{2NR}$$

where p is the probability of PrEP adherence, x_1 is the indicator of first-line treatment (0 for SMS, 1 for WhatsApp), and x_{2NR} is the indicator of the second-line treatment among non-responders to the first-line treatment (0 for monthly counseling, 1 for drug-level feedback). The linear predictors for each of the four embedded dynamic treatment regimes are:

Embedded dynamic treatment regime	Linear predictor
SMS, monthly counseling	β_0
SMS, drug-level feedback	$\beta_0 + \beta_2$
WhatsApp, monthly counseling	$\beta_0 + \beta_1$
WhatsApp, drug-level feedback	$\beta_0 + \beta_1 + \beta_2 + \beta_3$

Code: This analysis will compare the four embedded DTS using a ‘weighted and replicated’ approach (see above for details on why this approach is needed). Here, ‘responder’ means those who responded to 1st-line treatment.

- Weighting:
 - Assign a weight of 2 to responders and 4 to non-responders
 - Use robust SEs
- Replicating:
 - Replicate the data for each participant who responded to 1st-line treatment (i.e., they appear in the data twice)
 - Use a (weighted) GEE: $\log(p) = \beta_0 + \beta_1 x_1 + \beta_2 x_{2NR} + \beta_3 x_1 x_{2NR}$
 - Independence working correlation matrix
 - Each participant is a cluster
 - Log link function (to estimate RRs)
 - Predictors:
 - Indicator of 1st-line treatment (x_1)
 - 0 = SMS, 1 = WhatsApp
 - Indicator of 2nd-line treatment for non-responders to 1st-line treatment (x_{2NR})
 - 0 = monthly counseling, 1 = drug-level feedback
 - Interaction between 1st- and 2nd-line treatment
- SAS Code:
 - olddata = dataset
 - newdata = weighted and replicated data
 - R = indicator of response to 1st-line treatment
 - X1 = indicator of 1st-line treatment
 - X2 = indicator of 2nd-line treatment
 - y = indicator of response at 9 months
 - id = participant ID

```
data newdata; set olddata;
  if R=1 then do;
    ob=1; X2=0; weight=2; output;
```

```

        ob=2; X2=1; weight=2; output;
    end;
else if R=0 then do;
    ob=1; weight=4; output;
end;
run;

proc genmod data=newdata descending;
    class id;
    model y = X1 X2 X1*X2 / dist = poisson
                        link = log
                        ;

    scwgt weight;
    repeated subject=id / type=ind;

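### Primary Analysis 3 fixes the strategy weights at 2 and 4; this is valid, but weights estimated from the observed second-stage split would be more precise for strategies sharing a first-line arm

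*SAP*

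**What the plan says.** The Weighting paragraph of SAP Primary Analysis 3 derives the weights from the design: "assuming 1:1 randomization in each of the two phases of the SMART, the chance of a responder following the strategy is 0.5", and for a non-responder 0.25. It gives the aim as "However, all participants should be equally represented". The Code part then states "Assign a weight of 2 to responders and 4 to non-responders", and the SAS data step writes the constant on every non-responder row ("ob=1; weight=4; output"). Nothing adapts the weights to the split that actually occurs. The only other weighting in this analysis is for censoring, and it applies only if loss to follow-up passes the 10% triggers.

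Protocol section 4.2.4 describes the second randomization: "Randomization will be conducted with a ratio of 1:1 between the two study arms. We will use envelopes in order to assign" non-responders, and "site staff in Johannesburg will open the envelopes in the specified order only when they are ready to randomize" a participant. It does not say whether the list is blocked or stratified by first-line arm. Protocol section 6.4.1 says the four strategies will be ranked and mentions inverse-probability weighting without giving values.

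**The concern.** Fixed weights make everyone equally represented on average over repeated randomizations. In the sample in hand they do so only if the non-responders in each first-line arm divide exactly in half. When they do not, the strategy whose option received more non-responders is weighted towards non-responders, and its partner in the same arm is weighted towards responders. The two strategies share the same responders, so any difference in mix between them is chance.

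Month-2 response and the month-9 outcome are both TFV-DP thresholds, so responders and non-responders may well differ at month 9. In that case the chance difference in mix adds noise to the ranking and contrast of the two strategies. The observed allocation contains the information needed to remove it.

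**Working it through.** **Inputs from the documents.** Weights 2 and 4 (SAP Primary Analysis 3). From protocol section 6.3: 175 women per first-line arm, month-2 response 40% (two-way SMS) and 60% (WhatsApp), hence 105 and 70 non-responders; month-9 adherence among non-responders 40% vs 25% or 50% vs 30% (Table 2).

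**Assumption.** The documents give no month-9 adherence for month-2 responders. I use 60-80%, with 40-50% as a low case.

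**The plan's weights.** 1/0.5 = 2 and 1/(0.5 × 0.5) = 4. Both reproduce.

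**Form of the estimator.** The model is saturated, so each strategy estimate is a weighted mean. Let nR be the responders in the arm (yR adherent), nN the non-responders, n = nR + nN, and k the non-responders given the option (yk adherent).

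- Fixed weights: (yR + 2·yk)/(nR + 2k). The non-responder share is 2k/(nR + 2k), which equals nN/n only when k = nN/2.
- Estimated weights, 2 for responders and 2·nN/k for non-responders: (yR + nN·yk/k)/n. The non-responder share is nN/n for any k.

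The factor 2 is common to everyone within a first-line arm, so first-stage imbalance does no harm.

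**Worked case: SMS arm, 70 responders, 105 non-responders split 45/60.**

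- Non-responder shares under fixed weights: 90/160 = 56.3% and 120/190 = 63.2%. The actual share is 105/175 = 60%.
- Probability of a split this uneven or worse under simple 1:1 allocation: 2 × P(Binomial(105, 0.5) ≤ 45) = 0.172.
- Suppose 70% of responders are adherent (49 of 70) and 30% of non-responders on either option. Fixed weights give (49 + 2 × 13.5)/160 = 47.5% and (49 + 2 × 18)/190 = 44.7%, a gap of 2.8 points between options with identical results.
- The estimated weights are 2 × 105/45 = 4.67 and 2 × 105/60 = 3.50. They give (49 + 105/45 × 13.5)/175 = 46.0% and (49 + 105/60 × 18)/175 = 46.0%.

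**Validity of the fixed weights (simulation, 175 per arm).** Average bias is at most 0.1 percentage point, and 95% intervals from the robust standard error cover 94-95%.

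**Variance reduction from estimated weights (simulation, at least 200,000 trials per scenario), contrast of two strategies sharing a first-line arm.**

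| Second-stage list | Responders at month 9 | Reduction |
|---|---|---|
| Simple 1:1 | 60-80% | about 2-26%, median between 9% and 10% |
| Balanced overall, not within first-line arm | 60-80% | about 1-18%, median about 5% |
| Stratified by first-line arm | 60-80% | about 0% |
| Simple 1:1 | 40-50% | about -2% to 3% |

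For single-strategy rates under simple allocation with responders at 60-80%, the reduction is about -0.5% to 6% for the better second-stage option and about 2% to 11% for the worse one.

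**Effect of the standard error.** The power of the within-arm contrast, with responders at 70% and non-responders at 40% vs 25%, is:

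| Month-2 response | Fixed weights | Estimated weights, unmodified robust SE | Estimated weights, SE matching true spread |
|---|---|---|---|
| 40% | 0.350 | 0.339 | 0.369 |
| 60% | 0.215 | 0.194 | 0.258 |

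Across the settings checked, the unmodified robust standard error with estimated weights covers 96-98%. It is conservative and gives the gain away.

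**The case against.** The strongest reply is that nothing here is wrong. The weights are the known assignment probabilities, and the planned interval already covers chance imbalance. The 2.8-point gap in the worked case compares with a standard deviation of roughly 5.5 to 6 points for that contrast. This stands. A reader might infer that fixed weights bias Primary Analysis 3 or manufacture a false winner, but the negligible average bias and correct coverage rule that out.

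Primary Analysis 2 already compares the two second-stage options separately in each first-line arm, with no responder mix involved. This also stands. With estimated weights the within-arm strategy difference is simply nN/n times that comparison. It also means that, in the worked case, Primary Analysis 2 would show no difference while Primary Analysis 3 showed 2.8 points; estimated weights would make the two agree.

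The SAP code prints four strategy rates and one global test, not pairwise contrasts within an arm. That is so, and single-strategy rates gain less. But the analysis exists to identify the best strategy, and ranking two strategies in the same arm depends on their difference.

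A reader might also infer from section 4.2.4 that the second list was unstratified. The protocol is silent on this, and stratification by first-line arm would bring the gain to about zero.

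Finally, the gain depends on an undocumented responder rate. The response threshold is 500 fmol/punch and the outcome threshold 700, and the protocol's background reports falling adherence over time, so a small gap between responders and non-responders is possible. The gain then vanishes.

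**Conclusion.** The point holds as one of efficiency only. The design weights are valid; weights estimated within first-line arm are more precise for contrasts between strategies that share that arm, provided the second-stage list was not stratified by first-line arm and responders do better than non-responders at month 9. In the central scenarios under simple allocation the variance falls by a median of between 9% and 10%, about 5% in standard deviation. The gain can reach about 26%, or be nil or marginally negative. Contrasts across first-line arms gain less, in line with the single-strategy figures. No figure is offered for the global test, which was not simulated. This is a cheap refinement, not a correction the validity of the analysis depends on.

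**What to change.** In the Weighting paragraph and the SAS code of SAP Primary Analysis 3, keep weight 2 for responders. Within each first-line arm, give non-responders on option a the weight 2 × (re-randomized non-responders in that arm)/(those allocated to a). Multiply by the planned censoring weights when these are triggered, because allocation-based weights alone do not even out the mix if month-9 outcomes are missing unequally by option.

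Obtain confidence intervals and the global test by bootstrapping women within first-line arm, recomputing the weights in each resample, or by a stacked sandwich that accounts for estimating the weights. Changing the weights alone in the present GENMOD code would be conservative and would slightly lower power. The SAP should also state whether the second-stage list was blocked or stratified by first-line arm, since that determines whether there is anything to gain.

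The cost is a few lines of text and code and a bootstrap. No data, participants or covariates are needed. The downside is a negligible loss of precision if responders and non-responders turn out to have similar month-9 adherence.
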